17. Participant cannot refrain from taking medications/dietary supplements/herbals or substances that could modulate glucose metabolism, or are considered anabolic, or reduce weight (fat mass) in the opinion of the PI or Physician, starting two weeks prior to enrollment and over the entire course of the study. These include progestational agents,

steroids, growth hormone, dronabinol, marijuana, calcium-betahydroxy-betamethylbutyrate (CaHMB), free amino acid supplements and dietary supplements to aid weight loss.

18. Participant has hypothyroidism (TSH \geq 10 mIU/L) or hyperthyroidism (TSH $<$ 0.4 mIU/L).
19. Presence of any condition that, in the opinion of the Investigator, compromises participant safety or data integrity or the participant's ability to complete the study.
20. Because all women participating in this project will be post-menopausal, there will be no need for a pregnancy test prior to DEXA procedures. Females currently on hormone replacement therapy (HRT) can participate in the study if they have been on a stable dose of HRT for at least 6 months and will continue to be on HRT during the study.
21. Potential participants taking stable doses of medications for the last 30 days prior to screening for Blood pressure, cholesterol, GERD may be permitted to participate.
22. Participant becomes Covid-19 positive at any point during the study.

Resources Available

We attest that all AdventHealth Translational Research Institute faculty and staff will be trained, and this training will be documented as described in AdventHealth Translational Research Institute Work Instruction 031.100.015 Documentation of Protocol Training.

We will implement regular, ongoing discussions between the PI and coordinator as per the AdventHealth Translational Research Institute SOP 030.000.002 Oversight of Research Studies at the Translational Research Institute. The coordinator will review source and communicate with all applicable study team members involved in the study on a regular basis regarding reportable new information, implementing amendments, study progress, and quality assurance/control.

The AdventHealth Translational Research Institute facilities are state of the art and we have within our building all required resources and staff to execute the study. We have a medical oversight team, Medical Oversight Committee, as well as a Quality Committee to appropriately monitor and address adverse events.

Study Procedures

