Participants Recruitment and Screening

Males and females in the age ranges 65-90 years will be recruited from AdventHealth EMR, senior centers, television, radio, social media advertisements, text messaging, emailing, newsletters, and mass mailing lists from the Orlando, FL catchment area, and by contacting potential participants on the AdventHealth TRI's participant database.

Potential participants will be medically screened to determine good health and without any contraindication to exercise. Approximately equal numbers of men and women will be recruited. Neither race nor ethnicity will be exclusions.

We will recruit volunteers through public advertisement by placing advertisements in community newspapers and radio, as well as on social media. Individuals who respond to

the ads will be contacted by telephone for preliminary screening and will be given an opportunity to ask initial questions and be provided additional description of the study. Potential volunteers who seem to meet criteria will be scheduled for an outpatient examination at AdventHealth TRI. Informed, written consent will be obtained at the screening visit.

We anticipate ~400 phone screens to successfully enroll and complete 18 participants per group (anticipating 15 completers per group).

Consent Process

We attest that all study staff delegated the authority to obtain informed consent will follow “Investigator Guidance: Informed Consent (HRP-802)”, as well as “Investigator Guidance: Documentation of Informed Consent (HRP-803)”.

Non-English Speaking Participants

We will not be enrolling Non-English speaking participants due to the complexity of the visits, number of visits and length of the study. The participant population will be English speaking.

Participants who are not yet adults (infants, children, teenagers)

We are not enrolling participants who are not yet adults.

Cognitively Impaired Adults

We will not enroll cognitively impaired adults.

Adults Unable to Consent

We will not enroll adults who are unable to provide consent.

Documentation of Informed Consent Process

Documentation of the informed consent process is required to establish that the participant was accurately and adequately informed and that no study-related procedures were initiated prior to obtaining informed consent. A research team member will note in the source documentation the consent process, date consent was obtained, and that consent was obtained prior to initiating any research procedures.

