Exercise compliance will be monitored for exercise training 4 days per week (minimum of 32 total sessions). Aerobic training will be 30 minutes of brisk walking, jogging, cycle ergometry. Walking will be the primary mode of aerobic exercise given its widespread popularity and ease of administration across a broad segment of the older adult population. Walking will be at a moderate intensity and determined based on Heart Rate (50-70% of Maximal HR from most recent VO₂max) and rating of perceived exertion using Borg's scale (ranges from 6 to 20). Other forms of endurance activity (e.g., stationary cycling) will be utilized on a limited basis when regular walking is contraindicated either medically or behaviorally. This is the exercise regimen that has demonstrated substantial increases in muscle size and strength in elderly people. See "Appendix: Schedule of Activities" for a table description of the procedures that will be performed during PHASE II.

PHASE III – POST-INTERVENTION TESTING

Following the exercise training intervention, participants in the OS group will participate in post-intervention testing. The testing procedures are a subset of those performed during the pre-intervention testing period (PHASE I). A detailed description of the procedures can be found above. The testing procedures will be taken over a 2-week period following the exercise intervention. See "Appendix: Schedule of Activities" for a table description of the procedures that will be performed during PHASE III.

Study Duration

Estimated start date for enrollment is Sept 30, 2019. Active recruitment and testing will continue until the end of the funding period or until 15 participants per group have been recruited. The study is funded by the National Institute of Aging until 01/31/2024.

Materials of Human Origin: Collection, Preparation, Handling and Shipping

Materials of human origin will be collected in the manner described in the specific study visits section of this protocol.

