The primary purpose of this protocol is to understand the role of physical activity on BAT mass and circulating batokines, and how these variables relate to cardiac and physical function in older adults. A formal sample size calculation was not performed. Rather, we referred to published studies with similar experimental designs (determination of BAT mass by PET scan) as a guide for sample size determination. From the published literature we determine that an n=15 per group (active and sedentary) will provide sufficient statistical power to detect differences in BAT mass.

Statistical Analysis Plan

The analysis will involve multiple steps and draw on statistical methods ranging from simple descriptive statistics to the modeling of repeated measures outcome data accounting for potential missing observations. The major outcomes of the study, the BAT mass, circulating batokines, muscle mass, strength, power and quality, and VO₂max will be compared using an unpaired student t-test to explore baseline differences between older athletes and older sedentary groups. Additionally, repeated measures ANOVA will be performed on the dependent variables as a function of the exercise intervention in the older sedentary group. Multiple linear regression will be used to determine how BAT mass and circulating batokines explain variation in physical characteristics of muscle (strength, quality) and cardiovascular health (VO₂max). Sex will be explored as a biological variable.

Potential Risks and Benefits

Potential Benefits

Participants will likely receive no direct benefit from taking part in this research study.

Potential Risks

RMR/RQ. There is no physical risk associated with RMR/RQ. Other risks include a feeling of claustrophobia experienced by some participants while under the transparent “hood”.

Protection Against Risk:

- A member of the study staff will remain with the subject at all times to ensure his/her comfort.

Blood draws and Intravenous lines (lab samples and infusions, e.g.). There is a risk of pain, vasovagal syncope, hematomas, and/or infection at the blood draw site (low risk of serious AEs). The total volume of blood drawn is over the course of the study is approximately 372 mls.

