Participant Request for Withdrawal from Study

Participation in this study is voluntary. Participants may decide not to participate in this study or may withdraw from this study at any time without penalty or loss of benefits.

Data Collection and Follow-up for Withdrawn Participants

Participants who request withdrawal or who are withdrawn by the PI from the study will have their data maintained in the research database. This data and biospecimens from the

withdrawn participant may be included in subsequent analysis. Participant withdrawal of biospecimens is not an option.

Adverse Event Reporting

Adverse Events

An adverse event (AE) is defined as both an expected side effect that is of a serious nature, or an unexpected side effect/event regardless of severity. Each participant is evaluated for adverse events at every study visit. Any event that is reported to the study staff and which meets the criteria of an adverse event will be documented as such and graded as to its attribution (unrelated to protocol, or possibly, probably, or definitely related to protocol) and severity (mild, moderate, or severe).

Recording of Adverse Events

At each contact with the participant, the investigator will seek information on adverse events by specific questioning and, as appropriate, by examination. Information on all adverse events will be recorded immediately in the source document, and also in the appropriate adverse event module of the case report form (CRF). All clearly related signs, symptoms, and abnormal diagnostic procedures results will be recorded in the source document.

Notification of Adverse Events

Adverse events will be reported according to AdventHealth Orlando IRB guidelines.

Safety Monitoring Plan

Safety Monitoring

Research and safety data will be reviewed by the PI. This review will take place at regular meetings with the clinical coordinator and medical investigator where the safety labs for each new participant will be reviewed. Other items discussed will include: progress or adverse events occurring in the following: participant confidentiality, participant recruitment, and consent process. All will monitor response to tolerance of and effectiveness of the exercise program.

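### The named repeated measures ANOVA does not deliver the promised handling of missing data, and no fixed rule keeps baseline data in the analysis after a later withdrawal or Covid-19 exclusion

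*Combined protocol and SAP*

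**What the plan says.** The Statistical Analysis Plan opens by saying that the methods will extend to "modeling of repeated measures outcome data accounting for potential missing observations". It then names two analyses that bear on missing data. The major outcomes "will be compared using an unpaired student t-test to explore baseline differences between older athletes and older sedentary groups". For the effect of training, "repeated measures ANOVA will be performed on the dependent variables as a function of the exercise intervention in the older sedentary group". No mixed model, imputation, analysis set or sensitivity analysis is named. Under Phase III, only "participants in the OS group will participate in post-intervention testing", so each outcome has one pre value and one post value, in one group.

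Three other places decide whose data reach these analyses:

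- **Data Collection and Follow-up for Withdrawn Participants.** Participants "withdrawn by the PI from the study will have their data maintained in the research database", and so will those who ask to leave. Data and specimens from a "withdrawn participant may be included in subsequent analysis". The section does not say when, for which analysis or by whose decision.
- **Exclusion Criteria, item 22.** "Participant becomes Covid-19 positive at any point during the study". Nothing is said about data collected before the positive test.
- **Participants Recruitment and Screening.** The plan is for 18 per group, "anticipating 15 completers per group".

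**The concern.** The stated aim and the named method do not match. A reader who follows the named method will fit a paired comparison and lose every sedentary participant without a post-training value, although the same paragraph says that missing observations will be accounted for.

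The athlete–sedentary comparison needs no post-training value at all. BAT imaging, lipokine plasma, DEXA and VO₂max are collected at Visit 1, and strength and power at Visit 2. Someone who withdraws or tests positive in week 5 of training has already supplied all of these. Permissive wording on withdrawn data, and an eligibility-style exclusion that can be triggered on any study day, leave it open whether those values are analysed.

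Two things are at stake. Data may be discarded for reasons unrelated to the comparison, in groups of about 15. And the decision to use or omit them can be taken after the results are known. The section on investigator withdrawal also lets the PI remove someone for not following instructions, so in the sedentary group removal could be related to how training went.

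**Working it through.** The plan gives no alpha, power, effect size or SD, and states that no formal sample size calculation was done, so its claim of sufficient power cannot be reproduced. Its counts do agree: 2 × 18 = 36, the site total, and 18 − 3 = 15 completers. The implied loss is 3/18 = 16.7%, which is back-calculated and not stated.

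**1. ANOVA with one group and two time points.** The test of time has F(1, n − 1) = t², where t is the paired t statistic. The classical form uses complete pairs only. At an assumed two-sided 5% and 80% power, the detectable standardised change is 0.70 with 18 pairs and 0.78 with 15.

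**2. Precision gained by a likelihood model (OS change).** Assume unit variances, pre/post correlation r, 18 baselines, 15 pairs and random loss.

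- Complete pairs: variance = 2(1 − r)/15
- Likelihood: variance = (1 − r²)/15 + (1 − r)²/18
- r = 0.5: 0.0667 against 0.0639, a reduction of 4.2%
- r = 0.9: 0.01333 against 0.01322, a reduction of 0.8%

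These formulas ignore the estimation of the regression slope. A simulation of 10,000 runs that includes it gave standard errors of 0.261 (complete pairs) and 0.256 (likelihood) at r = 0.5, and 0.114 and 0.115 at r = 0.9. The gain is thus about 0–4%.

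**3. Bias if dropout depends on baseline.** If the three dropouts start 1 SD below completers, the completers' baseline mean exceeds the full-group mean by 3/18 = 0.167 SD. The bias in mean change is (r − 1) × 0.167: −0.083 SD at r = 0.5 and −0.017 SD at r = 0.9.

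Extreme case, simulated with the three lowest baselines always lost:

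| r | Bias, complete pairs | Bias, likelihood | SE, complete pairs | SE, likelihood |
|---|---|---|---|---|
| 0.5 | −0.140 | 0.001 | 0.256 | 0.268 |
| 0.7 | −0.085 | −0.001 | 0.200 | 0.210 |
| 0.9 | −0.028 | 0.001 | 0.115 | 0.123 |

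The bias goes, at a small cost in standard error. Root mean squared error, √(bias² + SE²), is 0.292 against 0.268 at r = 0.5, and 0.118 against 0.123 at r = 0.9.

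**4. Baseline OA–OS comparison.** With a two-sample t-test at the same assumed alpha and power (noncentral t), the detectable difference is 1.06 SD at 15 per group and 0.96 SD at 18. For a true difference of 1.0 SD, power is 75% and 83%. The figure of 0.96 is a best case. It requires all three losses in each group to occur after the baseline measurement and to be ones that would otherwise have been discarded. The site section counts 36 including screenings, so some of the 18 may never have a Visit 1.

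**5. Time at risk after baseline.** From the Schedule of Activities, Visit 1 is day −26, Visit 2 is day −19, the overnight Visit 3 ends on day −6, and OS testing ends on day 71. The OA row of the table is broken in the text. That OA finish at Visit 3 is read from OS-only post-testing and from OA payments stopping there.

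- After Visit 1: OS 71 + 26 = 97 days; OA 26 − 6 = 20 days; ratio 4.9
- After Visit 2: OS 71 + 19 = 90 days; OA 19 − 6 = 13 days; ratio 6.9

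**The case against.** The strongest reply is that the documents do not say what a critical reader might infer from them. Four such readings are tempting, and none is supported as fact.

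- *The SAP deletes incomplete pairs.* It does not say so. Deletion is a property of classical repeated measures ANOVA, and the opening sentence may mean that a model using all data is intended. The defect is a named method that does not match the stated aim.
- *Data from Covid-positive participants are optional or removed.* Item 22 contains no data rule. Items 20 and 21 of the same list are permissions, so the list is loosely drafted. If item 22 means withdrawal, the data are kept. What stands is that no rule is written.
- *The baseline t-test is limited to completers.* Completers appear as a recruitment target, and the endpoint section speaks of 15 participants per group. The t-test shrinks only if withdrawn participants' baselines are left out under the permissive wording.
- *Loss will be unequal between groups.* Time at risk is unequal, but the recruitment section anticipates the same fall from 18 to 15 in both. Unequal loss is a risk only.

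It can also be said that a mixed model is close to a matter of preference here. On precision, that stands. On bias, it stands if dropout is unrelated to baseline or if r is high. The documents give no evidence either way, and specifying the model now costs nothing.

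Finally, Visit 1 does not complete a participant's baseline. Strength and power come at Visit 2, and group status rests partly on accelerometry uploaded at Visit 2 or 3. This stands, and the fix allows for it.

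**Conclusion.** The concern holds as a mismatch and a missing rule. The one pre/post method named does not, as classically run, account for missing observations, and nothing guarantees that baseline data survive a later withdrawal or Covid-19 exclusion. It is worth correcting because the choice otherwise stays open until results are known, not because much power would be recovered.

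For the sedentary group's change, the precision gain is negligible to small, and the protection is against bias of the order of 0.1 SD under baseline-dependent dropout. The 0.08 SD figure is one scenario and not an upper bound. For the baseline comparison, the improvement from 1.06 to 0.96 SD is a ceiling. All of these figures rest on assumptions that the plan does not supply: alpha, power, the pre/post correlation, 3 of 18 lost, and the pattern of dropout.

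**What to change.** 1. **Baseline analysis set.** State that each OA–OS baseline comparison includes every eligible, group-classified participant who has that measurement (Visit 1 for MRI, plasma, DEXA and VO₂max; Visit 2 for strength and power), whatever happens afterwards. Say how participants without accelerometry confirmation of their group are handled.
2. **Withdrawn and Covid-positive participants.** In the section on withdrawn participants, change *may* to *will* for data collected before withdrawal. Apply the same data rule to participants who become Covid-19 positive after enrolment. This concerns use of data only and leaves their clinical management as it is.
3. **Pre/post model.** Replace the repeated measures ANOVA with a likelihood-based mixed model for the two time points (fixed effect of time, unstructured covariance) on all OS participants with any measurement. State the missing-at-random assumption, and report the completers-only paired analysis as a sensitivity analysis. With no missing values, the estimated mean change is the same as in the paired analysis.

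The cost is a wording change to the protocol and SAP. No extra visits, participants or data are needed.

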Waiver of Written Documentation of Consent or Waiver of Consent

N/A

Randomization

N/A

Study Visits

All study visits will be conducted at the AdventHealth Translational Research Institute.

PHASE I – SCREENING AND PRE-INTERVENTION TESTING

Both older athlete and older sedentary groups will undergo the screening and pre-intervention testing phase. See “Appendix: Schedule of Activities” for a table description of the procedures that will be performed during PHASE I.

Screening: SV1

Approximate visit time: ~ 3 1/2 hours

Volunteers will arrive, after an 8 hour overnight fast, to the AdventHealth TRI. Following voluntary written informed consent, all research participants will undergo a screening process for eligibility. This process may be repeated if necessary, under the discretion of the Medical PI. The following listed below procedures will be performed:

Demographics, Medication & Medical History, Physical Examination, Vital Signs, and Anthropometrics will be obtained. A full physical examination will be performed by a study physician, physician assistant, or nurse practitioner and will include general assessment of the following: head, ears, nose, eyes, throat, heart, lungs, abdomen, extremities, skin, neurological functioning, and any other impressions or problems noted by the provider at the time of exam. This will also include height, weight (metabolic), BMI, blood pressures, heart rate, respirations, temperature, medication, supplement history and a basic assessment of cognitive functioning via the Mini Mental State Examination (MMSE).

Electrocardiogram (ECG). A standard 12-lead ECG will be performed. Electrodes will be placed on the chest to provide a tracing of the electrical activity of the heart.

Physical activity questionnaires will be administered at screening. The Exercise History and Physical Activity Scale for the Elderly (PASE) are instruments that measures the level of habitual physical activity for individuals. The CHAMPS Physical activity health questionnaires will also be administered at screening. The MMSE will be administered at this time too.

Fasting blood draw to measure: a lipid panel; Complete Metabolic Panel (CMP); Complete blood count with differential (CBC w/ diff); TSH and HbA1c. Total blood volume for screen labs 14mls. Safety labs may be repeated per Investigator discretion, if needed. Blood draws may also take place at visit 2 or visit 3.

Urine collection for urinalysis.

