Waist Circumference Measurements which are a surrogate measure of abdominal fat will be conducted during screening. The Gulick II tape measure will be used for accuracy in obtaining duplicate waist measurements. All circumferences will be measured in centimeters directly on the skin.

Hand-Grip Strength Test. All participants will perform a hand grip test that will be conducted three times with 1 minute of rest between each repetition using the dominant hand of each participant. The greatest grip strength and the average of the three tests will be recorded.

Lower extremity performance battery. The Short Physical Performance Battery (SPPB) is a brief performance-based test that will be used to measure lower extremity performance. The SPPB consists of three tasks: five repeated timed chair stands, timed standing balance (with feet in parallel, semi-tandem, and tandem positions), and a 4-meter walk to determine usual gait speed.

Step Test: Each participant will be asked to complete a timed step test.

Covid Testing: Participant must have a negative covid test 1 week prior to the next visit. Covid testing may take place on a separate visit when SV1 is not within 1 week of V1.

Screening tests may be repeated if the Investigator deems necessary.

Visit 1

Approximate visit time: ~ 3 hours

Review of Adverse Events, Concomitant Medications

Vital Signs

Body Weight

3-Day Food Diary: Participants will be given a food diary and asked to record what foods and drinks they eat over a 3-day period. Participants will return the completed diary on visit 2.

Fasting blood draw to collect EDTA plasma. Circulating lipids related to BAT activity and mass will be measured in plasma samples. Total blood volume will be 10 mls. Safety labs may be repeated per Investigator discretion, if needed.

MR Imaging for BAT Mass. Brown adipose tissue will be differentiated from white adipose tissue using fat fraction and T2* relaxation time maps generated from a commercially available modified 6-point Dixon (mDixon) water-fat separation method. MRI scans will be performed on a Philips 3T using axial, coronal, and sagittal slice orientations to provide anatomical reference scans in the neck and body area. Quantitative mDixon scans will be used for calculating proton density fat fraction (PDFF) maps. The participant may be removed from the magnet and repositioned during the exam in order to determine the same day variability of this method.

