Hyperinsulinemic-Euglycemic Clamp: The glucose clamp is the gold standard for measurement of insulin sensitivity and will be performed as previously described by our group (1, 5, 9, 10). After an overnight 8-hour fast, an intravenous catheter will be placed in the vein for infusion of insulin and glucose. A second catheter will be placed in the vein of the contra-lateral arm for blood withdrawal. After baseline blood is collected, a primed (210 mg/m²), continuous (2 mg/min/m²) infusion of [6,6-2H₂] glucose will be initiated for assessment of endogenous glucose production. A 2-step euglycemic clamp will be started with a 2-hour infusion of insulin (Humulin-R) at 15 mU/m²/min, followed by 2 hours at 40 mU /m²/min. Plasma glucose will be measured at 5-10 min intervals via NOVA StatStrip Glucose Meter. Plasma glucose will be allowed to either decrease to ~90 mg/dl or will be increased to ~90 mg/dl in each participant depending on the fasting blood glucose levels. Euglycemia (~90 mg/dL) will be maintained with a variable 20% dextrose infusion enriched with [6,6-2H₂] glucose. Rates of glucose disposal (M) and endogenous glucose production (EGP) will be calculated by non-steady-state equations based on plasma [6,6-2H₂] glucose enrichment determined by gas chromatography mass spectrometry. A baseline blood sample will be collected prior to -30 mins. Then three blood samples will be collected for determination of plasma insulin, free fatty acid (FFAs), C-Peptide, and glucose concentrations prior to the insulin infusion, and at the beginning of each steady state and every 10 minutes during the two steady state portions of the clamp which will last approximately 4 hours from the time at which the insulin infusion is initiated (-30min, -20min, -10min, 0min, +30min, +60min, +100min, +110min, +120min, +220min, +230min, and +240min). Participants will complete a 24-hour urine collection on days where hyperinsulinemic-euglycemic clamps are run. Total blood volume during this procedure will be approximately 192 mls.

Calculations: Hepatic glucose production is expected to be completely suppressed at this level of insulin, even in diabetic subjects. In this case, peripheral glucose uptake (R_d) should equal the glucose infusion rate (GINF) during steady state (the last 30 minutes of each step of the clamp) after correction for urinary glucose loss.

That is: - R_d = Steady State GINF - urinary glucose loss

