Appendix: Schedule of Activities

	Phase I: Pre-Intervention					Phase II: Intervention								Phase III: Post-Intervention					
	Screening	Baseline				V 4-7	V 8-11	V 12-15	V 16-19	V 20-23	V 24-27	V 28-31	V 32-35	Exercise Extension (prn)	V 36	V 37	V 38	V 39	
Visit	SV1	V1	V2	V3		D 0* - D 3	D 7 - D 10	D 14 - D 17	D 21 - D 24	D 28 - D 31	D 35 - D 38	D 42 - D 45	D 49 - D 52		D 56	D 60	D 64	D 70	D 71
Day	D -54	D -26	D -19	D -7	D -6														
Windows **	within 28 days of V1+2d	±2	±2	±4		CRU overnight	Wk 1	Wk 2	Wk 3	Wk 4	Wk 5	Wk 6	Wk 7	Wk 8	*Wk 9-11	+3	±2	±3	±2
OA Group	X	X	X	X	X	X/EOS	X	X	X	X	X	X	X	X		X	X	X	X/EOS
OS Group	X	X	X	X	X	X	X	X	X	X	X	X	X	X		X	X	X	X
Informed Consent	X																		
Inclusion/Exclusion Criteria	X																		
Demographics	X																		
Past Medical History	X																		
Concomitant Medication/Supplements	X	X	X	X	X	X	X	X	X	X	X	X	X	X	X	X	X	X	X
Physical Examination	X															X			
Adverse Events	X	X	X	X	X	X	X	X	X	X	X	X	X	X	X	X	X	X	X
Height	X			X													X		
Weight (metabolic)	X	X	X	X	X	X										X	X	X	X
BMI	X															X			
Waist circumference	X															X			
Vital Signs (BP, Pulse, Respiration, Temp)	X	X	X		X											X	X	X	X
ECG (12-lead)	X															X			
Study Specific Questionnaires:																			
MMSE, PASE, CHAMPS, Exercise History	X																		
Blood Collection: Lipid Panel, CMP, CBC with differential, TSH, HbA1c	X															X			
Blood Collection: EDTA Plasma (for		X															X		
Covid testing	X*		X*													X*		X*	
Urine Collection	X																		
Handgrip strength	X															X			
SPPB	X															X			
Step Test	X															X			
Dispense 3 Day Food Diary	X																X		
Collect 3 Day Food Diary			X														X		
MRI	X																X		
DEXA	X															X			
VO2max test/stress test	X															X			
Placement of Accelerometers	X																X		
Collect Accelerometers		X*	or X													X*	or X		
Echocardiogram		X														X			
1-RM Muscle Strength	X															X			
Biodex	X															X			
Blood Collection: POC Glucose (clamp prep)			X														X		
Dinner Meal Consumption			X														X		
24-hr Urine Collection					X													X	
Hyperinsulinemic-Euglycemic Clamp					X													X	
RMR/RQ					X														X

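### The stated study-wide blood volume of about 372 mL cannot be reproduced from the protocol's own draws, which come to 418–432 mL for older sedentary (OS) participants

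*Combined protocol and SAP*

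**What the plan says.** The total is in Potential Risks, under blood draws and intravenous lines: "The total volume of blood drawn is over the course of the study is approximately 372 mls". It names no group.

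The component volumes are in the Phase I visit descriptions:

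- Screening (SV1): "Total blood volume for screen labs 14mls".
- Visit 1, EDTA plasma: "Total blood volume will be 10 mls".
- Visit 3, Hyperinsulinemic-Euglycemic Clamp: "Total blood volume during this procedure will be approximately 192 mls".

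On who has which draws, the Phase I section says: "Both older athlete and older sedentary groups will undergo the screening and pre-intervention testing phase". The Phase III section says: "Following the exercise training intervention, participants in the OS group will participate in post-intervention testing". It adds that these tests are part of the Phase I set and refers back to the earlier descriptions for the detail. Research Design lists the clamp, and fasting glucose and lipids, among the outcomes measured both before and after the intervention, and it has batokine blood drawn at both times. In the Schedule of Activities, three rows each carry one mark before and one after the intervention: the lab panel ("Blood Collection: Lipid Panel, CMP, CBC with differential, TSH, HbA1c"), the EDTA plasma and the clamp.

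**The concern.** A whole-study total should follow from the volume of each draw and the number of draws. Here it does not, for either group. The 372 mL figure is the only whole-study blood volume in the risk section, and the participants are 65 to 90 years old. If 192 mL per clamp is right, the section understates what OS participants give. If 372 mL is right, a component volume is overstated or a smaller Phase III draw has gone unstated. A reader cannot tell which exposure was meant. The sample size, the endpoints and the analysis do not depend on it.

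**Working it through.** **Inputs.** Lab panel 14 mL (Screening), EDTA plasma 10 mL (Visit 1), clamp about 192 mL (Visit 3), stated total about 372 mL (Potential Risks). The number of draws comes from the Phase III section and the Schedule of Activities. Discretionary repeat labs and finger sticks have no stated volume and are left out; they could only add to the sum.

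**Assumption.** No Phase III volume is given. Each repeat draw is taken to have its Phase I volume.

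**Trying to reproduce 372 mL.** Sum of volume × number of draws:

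| Reading | Sum (mL) | Difference from 372 |
|---|---|---|
| Phase I only (OA) | 14 + 10 + 192 = 216 | −156 (−41.9%) |
| OS, all three draws twice | 2 × 216 = 432 | +60 (+16.1%) |
| OS, no Phase III lab panel | 216 + 10 + 192 = 418 | +46 (+12.4%) |
| Two clamps and nothing else | 2 × 192 = 384 | +12 (+3.2%) |
| 192 mL covering both clamps, labs and EDTA twice | 2 × 14 + 2 × 10 + 192 = 240 | −132 (−35.5%) |

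A search over 0–3 lab panels, 0–3 EDTA draws and 0–2 clamps found no combination that equals 372 mL.

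The schedule implies 432 mL, because the lab-panel row is marked again in Phase III. The 418 mL figure is a cautious lower bound that drops that repeat. The two-clamp row does not depend on that choice: at 192 mL each, the clamps exceed the total before any other blood is counted.

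**What would give 372 mL in OS.**

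- Equal clamps, labs repeated: (372 − 2 × 24) / 2 = 162 mL each, which is 30/192 = 15.6% below the stated volume.
- Equal clamps, labs not repeated: (372 − 14 − 10 − 10) / 2 = 169 mL each, which is 23/192 = 12.0% below.
- First clamp at 192 mL and a smaller second one: 372 − 216 = 156 mL is left for Phase III. The second clamp would then be 156 − 24 = 132 mL with labs, or 156 − 10 = 146 mL without.

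None of these clamp volumes appears in the protocol. The 162 mL case fits exactly, which would be consistent with one entry having been changed without the other. That is an inference only.

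**The case against.** The protocol states volumes for Phase I alone, and these sum to 216 mL; everything above that comes from carrying them into Phase III. A second clamp of 132 or 146 mL would leave every stated figure literally true. Both 192 and 372 mL are given as approximate, and two clamps differ from the total by only 3.2%. The practical consequence is small, since the draws are spread over about 120 days.

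Part of this stands. The 46–60 mL gap depends on equal volumes, and the clamp entry need not be wrong if 372 mL is right. But the Phase III section refers back to the Phase I descriptions, and no shorter or smaller second clamp is described, so equal volumes are the natural reading. Rounding could explain 384 against 372 mL only if every other scheduled draw were close to zero; it does not cover 12–16%. The limited consequence sets the severity and does not make the figures agree.

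**Conclusion.** The concern holds, as a minor point. The stated total of about 372 mL cannot be obtained from the protocol's own draws. For OS participants the sum is 418–432 mL, 12–16% above the stated figure, provided Phase III draws have the Phase I volumes and discretionary draws are excluded. At the stated 192 mL, two clamps alone exceed the total. For OA participants, who have Phase I testing only according to the Phase III section, the sum is 216 mL. The single figure may be meant for the longer OS pathway, so the OA difference is not counted as an error. The mismatch is certain; which entry is at fault is not, because the clamp section lists sampling times but no volume per sample. No stated limit is breached.

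**What to change.** First check the volume per clamp and each Phase III draw volume against the clamp draw sheet. Then make the clamp section and the Potential Risks total agree with each other and with the 14 mL and 10 mL entries:

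- If 192 mL applies to both clamps, change the total to about 216 mL for OA and 418–432 mL for OS, settling the OS figure once the Phase III labs are confirmed.
- If 372 mL is right for OS, correct the clamp volume, or state the smaller Phase III volume if the second clamp differs.

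Give the total by group and say that discretionary repeats are excluded. Any participant-facing text, which was not available for this review, should carry the same reconciled figure. The cost is about one line of correction after one look at the draw sheet, with no change to design or analysis.
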